Media Academy Cymru's (MAC) Cerridwen Project. A randomised control trial efficacy study with internal pilot.

Cordis Bright

Principal investigators: [name], [name], [name], [name], [name], [name], [name]

Media Academy Cymru's Cerridwen Project

Statistical analysis plan

Evaluating institution: Cordis Bright

Principal investigator(s): [name], [name], [name], [name], [name], [name], [name]

Project title	Media Academy Cymru's (MAC) Cerridwen Project. A randomised control trial efficacy study with internal pilot.	
Developer (Institution)	Media Academy Cymru	
Evaluator (Institution)	Cordis Bright	
Principal investigator(s)	[name], [name], [name], [name], [name], [name], [name]	
SAP author(s)	[name], [name], [name], [name], [name], [name]	
Trial design	Two-armed parallel randomised control trial with random allocation at the young person level	
Trial type	Efficacy trial with internal pilot and implementation and process evaluation	
Evaluation setting	The intervention is delivered at a variety of safe spaces in the young people's community	
Target group	10- to 17-year-olds in Cardiff, Swansea, Merthyr Tydfil and Caerphilly who are at risk of involvement in serious violence or exploitation	

Number of participants	596 (298 in treatment group, 298 in control group)
Primary outcome and data source	Self-reported offending (volume score on the Self-Reported Delinquency Scale) (See, Smith & McVie, 2003)
Secondary outcome and data source	Empathy (Basic Empathy Scale) (Jolliffe and Farrington, 2006) Pro-social values and behaviour (SDQ – Pro-social behaviour subscale) (Goodman, 2005) Behavioural difficulties (SDQ – externalising behaviours score (combining conduct problems and hyperactivity/inattention subscales)) (Goodman, 2005)

1 SAP version history

Version	Date	Changes made and reason for revision	
1.2 [latest]			
1.1	Revised May 2025	Changed SDQ scale from conduct problems subscale to externalising behaviours score (combining conduct problems and hyperactivity/inattention subscales) Reason: We agreed to change our approach during the internal pilot Updated delivery area to include Caerphilly	

		Reason: We, MAC and YEF agreed an expansion of the delivery area as part of the internal pilot
		Added further modelling into sample size calculations
		Reason: To reflect learning from the pilot period
1.0 [original]	Published March 2025	[leave blank for the original version]

2 Table of contents

1	SAP	version history	2
2	Tab	le of contents	4
3	Intr	oduction	5
4	Trial	design	6
	4.1	Overview	6
	4.2	Research questions	9
	4.3	Outcomes	9
5	Sam	nple size calculations	12
	5.1	Overview	12
6	Anal	ysis	15
	6.1	Overview	15
	6.2	Primary outcome analysis	15
	6.3	Secondary outcomes analysis	17
	6.4	Subgroup analyses	18
	6.5	Further analyses	19
	6.6	Interim analyses and stopping rules	20
	6.7	Imbalance at baseline	21
	6.8	Missing data	22
	6.9	Compliance	23
	6.10	Intra-cluster correlations (ICCs)	23
	6.11	Presentation of outcomes	24
7	Refe	erences	26

3 Introduction

This is the statistical analysis plan (SAP) for an efficacy study including a two-armed parallel randomised controlled trial (RCT) and implementation and process evaluation of Media Academy Cymru's (MAC) Cerridwen programme. This plan should be read in conjunction with the study trial protocol, which is available at: https://youthendowmentfund.org.uk/wp-content/uploads/2024/07/MAC-Cerridwen-Evaluation-Protocol.pdf ¹

The Cerridwen programme is a six-month voluntary, one-to-one mentoring and case management intervention, rooted in cognitive behavioural approaches. The programme is working with young people living in the areas of Cardiff, Swansea, Merthyr Tydfil and Caerphilly in South Wales between April 2024 and April 2026.

Through a youth work approach, Cerridwen aims to reduce children and young people's future engagement in violence and offending behaviour by enhancing young people's empathy, building their emotional resilience, improving wellbeing, and challenging negative narratives. For a full list of the programme's intended short-term, medium-term, and long-term outcomes, please see the trial protocol.

The rationale for an efficacy RCT of Cerridwen is strong; in the UK there is limited robust evidence for what works to reduce offending among children and young people, and more research is needed for mentoring programmes with a specific focus on children and young people already involved in crime or violence. An efficacy RCT of Cerridwen will therefore contribute to knowledge and understanding of what works to reduce offending for this cohort. More information on the study rationale and background is available in the trial protocol.

The efficacy RCT which included an internal pilot (more about this can be viewed in the study trial protocol) started in April 2024, and will run until July 2026, with final reporting taking place in December 2026.

The evaluation team is collecting a range of data throughout the trial, including:

 Self-reported outcomes measures, including the Self-Reported Delinquency Scale (volume score subscale), the Social Support and Rejection Scale (full measure), the Basic Empathy Scale (full measure), and the Strengths and Difficulties Questionnaire (prosocial behaviour and externalising behaviours subscales).

-

¹ Last accessed 7 January 2025.

- Demographic data provided by MAC, including sex, age, race/ethnicity, involvement with other services, special educational needs and disabilities (SEND) data, and English as an Additional Language (EAL) status.
- Activity and monitoring data collected by the MAC delivery team.

This document sets out our planned analysis for each data type in more detail. The rest of this document is structured in the following way:

Section 4: Trial design sets out the research questions, key outcomes and measures, and randomisation approach for the trial.

Section 5: Sample size calculations presents the power calculations for the trial.

Section 6: Analysis sets out the approach to analysis of primary outcomes and secondary outcomes, subgroup analysis, exploratory analysis, further analysis, missing data, compliance and outcomes presentation.

4 Trial design

4.1 Overview

The efficacy study is a two-armed parallel RCT, comparing the effectiveness of a dedicated mentoring and case management programme (treatment group) to light-touch young person-led wellbeing and safety support (control group) in reducing children and young people's future engagement in youth violence and offending behaviours. All young people living in the areas of Cardiff, Swansea, Merthyr Tydfil and Caerphilly who are referred into the project, who are 10-17, who meet the eligibility criteria and who consent to be part of the evaluation are randomly allocated to either the treatment or control group on a 1:1 basis.²

Recruitment is taking place on a rolling basis between April 2024 and September 2025. MAC have established various referral routes in partnership with a range of key referral organisations including statutory and non-statutory organisations. These include (but are not limited to):

- Social Services (Children's Services).
- Schools and Pupil Referral Units.
- Youth Services.

.

² Young people are eligible for Cerridwen if they meet all three of the following inclusion criteria: (1) Young people are exhibiting or are at risk of exhibiting violent behaviours, (2) Young people are living in the areas of Cardiff, Swansea, Merthyr Tydfil or Caerphilly, and (3) Young people are willing to engage with and complete Cerridwen. For more detail, please see the evaluation protocol.

- Youth Offending Services.
- Voluntary and Community Sector Organisations.³
- Self-referrals including young people and parents/carers.⁴

Referral sources and the number of eligible and ineligible referrals are monitored and will be reported in the final evaluation report.

Randomisation is conducted at the individual (young person) level, without stratification, in randomly varying block sizes of four, six and eight young people. The randomisation sequence was generated using an online randomisation service (Sealed Envelope).⁵ Team members responsible for analysis were not involved in generating the randomisation sequence. For more information on the design of the randomisation process, please see the evaluation protocol.

Those recruited and randomly allocated to the treatment group receive weekly, two to three-hour one-to-one case management/mentoring sessions over a six-month period. Those randomly allocated to the control group receive light-touch, structured signposting and safeguarding support, provided by MAC. For more detail on the participant journey, please see the trial protocol.

Figure 1 below presents an overview of the trial design.

Figure 1: Trial design overview

Trial design, including number of arms		Two-arm parallel randomised control trial with random allocation at the young person level	
Unit of randomisation		Individual young person	
Stratification variables (if applicable)		None	
variable		Self-reported offending (violent or non-violent or general)	

³ Examples of organisations include: Atal Y Fro, Action for Children, Amber Project, Barnardo's, Fearless, Llamau, Platform, St Giles, The Hangout and Women's Aid.

⁴ Self-referrals may form a small proportion of overall referrals. Self-referrals will be subject to the same assessment of eligibility as other referrals. Eligibility and consent are re-confirmed in the first meeting with the young person to ensure only the intended cohort access Cerridwen.

⁵ See: https://www.sealedenvelope.com/. last accessed 10 January 2025.

Primary outcome	measure (instrument, scale, source)	Self-Reported Delinquency Scale (volume score)	
	variable(s)	Empathy Pro-social values and behaviours Behavioural difficulties	
Secondary outcome(s)	measure(s) (instrument, scale, source)	Empathy, measured by the Basic Empathy Scale (Jolliffe and Farrington, 2006). Pro-social values and behaviours, measured by the Strengths and Difficulties Questionnaire pro-social behaviour subscale (SDQ) (Goodman, 2005). Behavioural difficulties, measured by the Strength and Difficulties Questionnaire externalising behaviours scale (combining conduct problems and hyperactivity/inattention subscales) (SDQ) (Goodman, 2005).	
Baseline for	variable	Self-reported offending (violent and non-violent or general)	
primary outcome	measure (instrument, scale, source)	Self-Reported Delinquency Scale (volume score)	
	variable	Empathy Pro-social values and behaviours Behavioural difficulties	
Baseline for secondary outcome	measure (instrument, scale, source)	Empathy, measured by the Basic Empathy Scale. Pro-social values and behaviours, measured by the Strengths and Difficulties Questionnaire pro-social behaviour subscale (SDQ). Behavioural difficulties, measured by the Strength and Difficulties Questionnaire externalising behaviours scale (combining conduct problems and hyperactivity/inattention subscales) (SDQ).	

4.2 Research questions

The primary research question of the impact evaluation is:

Is a dedicated mentoring and case management programme delivered with children and young people involved in (or at risk of involvement in) youth violence and offending behaviours, focused on understanding and managing emotions, an effective approach to reducing children and young people's future engagement in youth violence and offending behaviours compared to light-touch young person-led wellbeing and safety support?

Secondary research questions are:

- 1. **Delivery:** Can the Cerridwen programme work under ideal circumstances?
- 2. **Impact:** a) What is the impact of the Cerridwen project? b) Do different subgroups of young people have different outcomes, e.g. those from minoritised/marginalised groups?
- 3. **Unintended consequences:** a) Does the Cerridwen project have any unintentional consequences? If so, what are these? b) Do different groups of young people experience these differently?
- 4. **latrogenic effects**: Are there any serious negative effects that can be attributed to the Cerridwen project on any outcomes?
- 5. **Mechanisms:** a) How does the Cerridwen project work to reduce young people's future engagement in offending? b) Which factors contribute most to the observed outcomes?

4.3 Outcomes

The primary outcome measure for the evaluation is self-reported offending as measured by the volume score on the Self-Reported Delinquency Scale (Smith & McVie, 2003) at baseline and T2, i.e., five months post-randomisation.⁶

About the SRDS Volume Score

⁶ Please note T2 data is collected at five months post-randomisation as the last (sixth) month of Cerridwen is aimed at supporting young people to exit the programme safely.

The SRDS is a 19-item self-reported delinquency scale developed as part of the Edinburgh Study of Youth Transitions and Crime (Smith & McVie, 2003). It covers a range of antisocial and offending behaviours, has been validated for use with young people in the UK, and has been used with those aged between 10 and 17. The volume score is the sum of the number of times that a young person reports involvement in the 19 different items.

The SRDS has been shown to have good psychometric properties; reported internal consistency is between .87-.92 with an inter-item correlation of .19 (Fonagy et al., 2018; Humayun et al., 2017) and the measure correlates with official police arrests (89.5% - 95.2%; McAra & McVie, 2005).

More information on the subscales, psychometric properties and validity of the SRDS is available in the YEF outcomes measures database (Youth Endowment Fund, 2022b)⁷ and in the YEF core measurement guidance (Youth Endowment Fund, 2021a and 2022a). ⁸

The secondary outcomes that we are investigating are:

- Empathy, measured by the Basic Empathy Scale (BES) at baseline and T2 (five months post-randomisation).
- Pro-social values and behaviours, measured by the Strengths and Difficulties
 Questionnaire (SDQ) pro-social behaviour subscale at baseline and T2 (five months
 post-randomisation).
- Behavioural difficulties, measured by the Strengths and Difficulties Questionnaire –
 externalising behaviours score at baseline and T2 (five months post-randomisation).

About the scales used to measure secondary outcomes

The **BES** is a 20-item self-report measure of empathy. It includes two subscales of affective and cognitive empathy. Each item is scored on a five-point Likert scale. A higher score reflects higher levels of empathy. The BES has convergent and divergent validity, and the Cronbach's alpha coefficients for the affective and cognitive empathy subscales is .79 and .85, respectively. More information on this scale, including psychometric properties and validity, is available in Jolliffe and Farrington (2006 and 2021).

-

⁷ See: https://youthendowmentfund.org.uk/outcomes/. Last accessed 9 January 2025.

⁸ See: <a href="https://res.cloudinary.com/yef/images/v1623145465/cdn/19.-YEF-SRDS-guidance/19.-YEF-SRDS-gui

The full **SDQ** is a 25-item questionnaire measuring behaviours, emotions and relationships for 4- to 17-year-olds. It contains five subscales:

- 1. Emotional symptoms.
- 2. Conduct problems.
- 3. Hyperactivity/inattention.
- 4. Peer problems.
- 5. Prosocial behaviour.

Each item is scored on a three-point Likert scale from 0 to 2, such that the scores for each subscale ranges from 0 to 10. For the prosocial values subscale high scores are desirable (i.e., greater prosocial values), but for the externalising behaviour scale (combining conduct problems and hyperactivity subscales) high scores are not desirable (i.e., a high score means greater externalising behaviours). The SDQ has been shown to have good internal consistency (Cronbach's alpha = .73), cross-informant correlation (mean=0.34), and retest stability after four to six months (mean: 0.62) (Goodman, 2001).

All primary and secondary measures were selected in agreement and collaboration with colleagues from MAC and YEF.

Data for all measures is collected directly from young people using either online survey software (SmartSurvey – see: https://www.smartsurvey.co.uk/) or a paper questionnaire at baseline and at five-months post-randomisation.

5 Sample size calculations

5.1 Overview

The primary objective of the Efficacy Study is to assess the effect of the Media Academy Cymru's (MAC) Cerridwen programme on self-reported offending as measured by the volume score on the Self-Reported Delinquency Scale (Smith & McVie, 2003). A sample size of 592 (296 per group), based on detecting a Minimum Detectable Effect Size (MDES) of 0.20 (equivalent to a 10% difference in proportions), assuming a correlation between baseline and follow-up of 0.5 (Humayun et al., 2019) and using a two-sided alpha of 0.05, would provide 80% power (Figure 2). Our assumptions about the MDES are informed by the YEF guidance (2021a) and previous research. For example, a meta-analysis using a random effects model (d=.21, 95% confidence interval, .07 to .34) of 18 studies, showed that mentoring programmes similar to Cerridwen make a 10-11% difference in relation to offending (Jolliffe & Farrington, 2008). We have also included the pre-post correlation based on values obtained from unpublished data from an RCT using the same outcome measure and in a similar population of adolescents (Humayun et al., 2019).

We have calculated the overall sample size for the trial a priori, in line with YEF guidance (2021a and 2021b). This is presented in the table below. The final sample for the trial will not be finalised until randomisation is complete in October 2025. We will update this table with the final figures once they are known.

These calculations were made with the Powerup! software package (Dong, N. and Maynard, R. A., 2013).

Figure 2: Sample size calculations

		Protocol	Randomisation
Minimum Detectable Ef	fect Size (MDES)	0.20	
	level 1 (participant)	0.5	
Pre-test/ post-test correlations	level 2 (cluster)	N/A	
	level 1 (participant)	N/A	

		Protocol	Randomisation
Intracluster correlations (ICCs)	level 3 (cluster)	N/A	
Alpha		0.05	0.05
Power		0.8	0.8
One-sided or two-sided	One-sided or two-sided?		
	intervention	296	
Number of participants	control	296	
	total	592	

The above table shows the Power Calculation for the study and suggests a total sample of 592 young people is required for a MDES of 0.20. However, we recognise that Cerridwen will need to receive more referrals than this to reach the target number due to anticipated attrition. We have worked closely with MAC colleagues taking into account YEF guidance to model target recruitment and retention rates needed to reach this sample of 592, factoring in an estimated attrition rate of approximately 10% from referral to recruitment, and a further 10% attrition from recruitment to completion of the intervention. This modelling suggests that the study needs to receive around 752 referrals to reach the final target sample size of 592. More information about modelled target recruitment and retention rates are available in the study protocol.

In the case of higher-than-expected attrition or lower-than-expected recruitment rates that result in the sample of 592 being exceeded or not reached, we have also calculated the possible MDES for different sample sizes in the table below. While the original modelling was based on estimated referral rates, updated recruitment and participation modelling informed by data from the internal pilot period suggests that a sample size of 367 is now more realistic. This would result in an MDES of 0.25. These estimates are based on the same approach, assumptions and software outlined above.

MDES	N recruited	Attrition %	N analysis
0.20	673	12	592
0.25	412	10	367
0.25	448	21	367
0.29	320	12	282
0.39	180	12	158
0.49	114	12	100
0.59	80	12	70

Based on: Pre-test/post-correlation of 0.50, p<.05, Power=.80, two-sided.

6 Analysis

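### One row of the Section 5.1 MDES table is inconsistent (448 recruited at 21% attrition leaves 354, not 367), and the front page and Section 5 give different target sample sizes (596 and 592)

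*SAP*

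**What the plan says.** Section 5.1 sets the target: "A sample size of 592 (296 per group), based on detecting a Minimum Detectable Effect Size (MDES) of 0.20", "assuming a correlation between baseline and follow-up of 0.5" and "using a two-sided alpha of 0.05, would provide 80% power (Figure 2"). Figure 2 repeats 592 (296 + 296) in its Protocol column and leaves the Randomisation counts to be filled in later.

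The section then explains that the pilot has changed expectations: updated modelling "suggests that a sample size of 367 is now more realistic", and the MDES attached to that number is 0.25. A table lists MDES, number recruited, attrition and number analysed, with the footnote "Based on: Pre-test/post-correlation of 0.50, p<.05, Power=.80, two-sided". Two of its rows lead to 367 analysed and an MDES of 0.25:

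- 412 recruited, 10% attrition
- 448 recruited, 21% attrition

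The other five rows all use 12% attrition.

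The summary table at the front of the SAP gives the number of participants as "596 (298 in treatment group, 298 in control group").

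**The concern.** The two rows ending in 367 describe the trial now expected. The 448 row says that 448 recruits still give an MDES of 0.25 after losing about a fifth of them. If that is wrong, a funder or delivery partner using the row would think the higher-attrition case slightly better protected than it is.

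The front-page figure raises a different problem. A reader who wants the planned sample size finds 596 in one place and 592 in another, with no explanation. The final report will compare achieved numbers with a target, so there should be only one.

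**Working it through.** **Inputs.** All come from Sections 4.1 and 5.1 of the SAP: two-sided alpha 0.05, power 0.80, 1:1 allocation, and a baseline to follow-up correlation of 0.5, so R² = 0.25.

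**Formula.** For an individually randomised trial with one baseline covariate:

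MDES = (t₀.₉₇₅ + t₀.₈₀) × √[(1 − R²) / (0.25 × N)] = (t₀.₉₇₅ + t₀.₈₀) × √(3/N), with N − 3 degrees of freedom.

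The choice of formula is an assumption about what the named software does. It is supported by the match below.

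**Step 1: reproduce the plan's own MDES figures.**

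| N analysed | Multiplier | √(3/N) | MDES computed | MDES in SAP |
|---|---|---|---|---|
| 592 | 2.806 | 0.0712 | 0.1998 | 0.20 |
| 367 | 2.809 | 0.0904 | 0.2540 | 0.25 |
| 282 | 2.811 | 0.1031 | 0.290 | 0.29 |
| 158 | 2.819 | 0.1378 | 0.3885 | 0.39 |
| 100 | 2.830 | 0.1732 | 0.490 | 0.49 |
| 70 | 2.843 | 0.2070 | 0.589 | 0.59 |

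Every pairing of MDES with number analysed reproduces to two decimals.

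**Step 2: check the attrition column.** Number analysed = number recruited × (1 − attrition).

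| Recruited | Attrition | Product | N analysed in SAP |
|---|---|---|---|
| 673 | 12% | 592.2 | 592 |
| 412 | 10% | 370.8 | 367 |
| 448 | 21% | 353.9 | 367 |
| 320 | 12% | 281.6 | 282 |
| 180 | 12% | 158.4 | 158 |
| 114 | 12% | 100.3 | 100 |
| 80 | 12% | 70.4 | 70 |

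The five 12% rows agree to the nearest whole number, which settles the convention the table uses. The 448 row misses by 13 (3.6% of 367). Rounding of the percentage cannot explain it, because even 20.5% attrition leaves only 448 × 0.795 = 356.

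**Step 3: what would make the 448 row consistent.**

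- Keep 448 and 367: attrition = 1 − 367/448 = 18.1%.
- Keep 21% and 367: recruits needed = 367/0.79 = 464.6, so 465.
- Keep 448 and 21%: 354 analysed, MDES = 2.809 × √(3/354) = 2.809 × 0.0921 = 0.259, which prints as 0.26.

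One possible source is inflating by multiplication: 367 × 1.21 = 444, which is near 448. The SAP does not say how the figure was reached, so this is a guess.

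**Step 4: power for an effect of 0.25.** By the normal approximation, power ≈ Φ(0.25/√(3/N) − 1.96).

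- N = 367: 0.25/0.0904 = 2.765, power 79.0%.
- N = 354: 0.25/0.0921 = 2.716, power 77.5%. The non-central t gives 77.3%.

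The row therefore overstates power for 0.25 by about 1.5 percentage points.

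**Step 5: the target N.** 298 + 298 = 596 and 296 + 296 = 592, so each figure is consistent within itself. They differ by 4 (0.7%). The MDES is 0.199 at 596 and 0.200 at 592, so power is unaffected in practice.

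**Step 6: neighbouring figures.**

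- The 412 row gives 371 at exactly 10%. Reaching 367 takes 1 − 367/412 = 10.9%, which rounds to 11%. At 371 the MDES is 0.253, so the row still supports 0.25.
- On referrals, the text says "This modelling suggests that the study needs to receive around 752 referrals to reach the final target sample size of 592", with losses of roughly 10% and then a further 10%. 752 × 0.9 × 0.9 = 609, and 592/0.81 = 731. Each gap is under 3%.

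**The case against.** The strongest reply is that nothing of substance moves. The SAP ties its MDES of 0.25 to 367 analysed, and that pairing is right. Only the joint case of 448 recruited and 21% lost changes the MDES, by less than 0.005, and the 596 against 592 discrepancy is under 1%. This stands as an argument about size. It does not make the row correct or reconcile the two targets.

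A reader might go further than the document allows in four ways:

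- **That the MDES of 0.25 is not delivered.** It is delivered at 367 analysed (0.254, printed to two decimals like the other rows), and the 412 row supports it too. The 596 and 752 figures have no bearing on it.
- **That 752 referrals is an error.** The text presents both the losses and the total as approximate. 752 is more than the stated losses require, so it errs on the safe side. The text's second loss runs to completion of the six-month programme, while the table's runs to the number analysed, and T2 is at five months, so the 10% and 12% need not be the same quantity. Section 5.1 leaves the detailed modelling to the protocol.
- **That recruitment is monitored against this table.** Section 6.6 refers to modelled target rates, which Section 5.1 places in the protocol. Its attrition trigger of 31% does not appear in the table.
- **That the SAP hides the loss of power for 0.20.** Section 5.1 states openly that 367, with an MDES of 0.25, is now the realistic case. Figure 2 labels 592 as the protocol figure and promises an update.

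**Conclusion.** Two figures are wrong as written, and both are minor. The 448 / 21% / 367 / 0.25 row contradicts the convention that the five 12% rows follow. On its own recruitment and attrition inputs it should read 354 analysed with an MDES of 0.26. The front page and Section 5 also give different target sample sizes.

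The MDES and power results assume the SAP's correlation of 0.5 and equal arms, and they ignore the site terms, as the SAP's own calculation appears to do. The attrition arithmetic needs none of these assumptions. The document does not show which of the three inputs in the 448 row was mis-stated, or whether 592 or 596 is the figure in the protocol.

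**What to change.** 1. **Correct the row.** If 448 and 21% are the modelled inputs, print 448 / 21% / 354 / MDES 0.26. If the modelled attrition is really 18%, print 448 / 18% / 367 / MDES 0.25. The sponsor's pilot modelling decides which.
2. **Use one protocol target** on the front page and in Section 5.1 and Figure 2. The power calculation as written supports 592 (296 per arm).
3. **Optional tidying.** Show the companion row as 412 / 11% / 367, and add a sentence reconciling the text's approximate 10% loss after recruitment with the table's 12%, or saying that they measure different things.

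The cost is a few words in the SAP, with no extra enrolment and no change to the analysis. Under the first option for the row, one stated MDES becomes slightly less favourable. The natural time is before the Randomisation column of Figure 2 is completed.
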